6.4 Primary Safety Endpoints

The study design evaluates the potential to substitute non-invasive for invasive FFR. Safety endpoints of the study include: 1. Evaluating the diagnostic accuracy of non-invasive FFR. If the end result demonstrates that the procedure is less accurate than invasive FFR, patients receiving this procedure, as an alternative to the current standard will be at greater risk. 2. Patients who undergo invasive procedures experience increased risk of infection or other comorbidities or complications, as compared to those who do not undergo invasive procedures. Therefore, if the noninvasive protocol results are not significantly different than the invasive results, patient safety might potentially be increased by using the noninvasive technology. 3. Noninvasive technology has the potential to reduce radiation exposure by reducing the number of invasive angiography and Stress MPI procedures necessary to complete patient evaluation. This increases patient safety relative to the adverse effects of radiation exposure.

7 Subject Selection and Withdrawal

7.1 Inclusion Criteria

1. Patients must be capable of giving informed consent.
2. Patients must be able to cooperate with technician performing the procedure.
3. Patients must have BMI <= 50.
4. Patients must have non-STEMI EKG without acute changes

5. *Patients must present to Lenox Hill Ambulatory CCTA Clinic with medically necessary appointment for CCTA for the purpose of evaluation coronary stenosis for the provisional diagnoses of chest pain or angina or angina equivalent.*
6. *Patient must be able to take nitroglycerin and beta blockers.*

7.2 Exclusion Criteria

Create a numbered list of criteria that would exclude a subject from study enrollment. If appropriate, should generally include that subjects cannot be homeless persons, or have active drug/alcohol dependence or abuse history. If exposure to certain medications or treatments at screening is prohibited, that must be noted in the exclusion criteria—if these are also prohibited concomitant medications during the study period that should be noted here as well.

7. *Patient must not have a history of coronary stenting or coronary artery bypass graft.*
8. *Patients must not have severe or end stage renal disease as diagnosed as eGFR < 50.*
9. *Patients must not have a BMI > 50.*
10. *Patients must not have active asthma requiring bronchodilator therapy.*
11. *Must not have any allergies to contrast.*

7.3 Vulnerable Populations

Indicate whether you will target any of these vulnerable populations.

- Children or viable neonate
- Cognitively impaired
- Pregnant Women, Fetuses or neonates of uncertain viability or nonviable
- Prisoners
- NSLIJ Employees, residents, fellows, etc
- poor/uninsured
- Students
- Minorities
- Elderly
- Healthy Controls

If any of these populations are included in the study, describe additional safeguards that will be used to protect their rights and welfare.

None of these vulnerable populations are targets of this study.

7.4 Subject Recruitment and Screening

Patients scheduled to present or presenting to the Lenox Hill Ambulatory Care CCTA Clinic for evaluation of coronary stenosis with the provisional diagnosis of chest pain or angina will be offered the opportunity to participate in this clinical trial. If possible, patients will be contacted in advance of the visit by the study coordinator and educated on the study. All eligible patients will receive education about the study and offered the opportunity to participate upon arrival to the clinic.

The study coordinator, cardiology fellow, or cardiologist will take the patient's medical history as it relates coronary stenting, CABG and other cardiac risk factors (including smoking, family history of heart disease, hyperlipidemia, diabetes, hypertension.) Routine preparation for CCTA will be conducted by clinic staff. As part of this activity patient height and weight will be obtained, and a blood draw for Serum Creatinine to calculate patient eGFR will be taken.

In order to assess the primary endpoint of comparison of event rates for patients treated with CCTA and FFR-CT, we will perform a retrospective chart review of Invasive Coronary Angiograms performed at Lenox Hill Hospital from 2014 to 2018. We will specifically review Cardiac Catheterization reports to screen patients and record data for cases where the indication for Catheterization was (1) Positive stress test and/or (2) Positive CCTA. Based on the catheterization report we will determine whether the patient had obstructive coronary artery disease with/without flow limitation, in the same manner and following the same definitions as those used to categorize level of obstruction in subjects enrolled in the prospective cohort of the study.

7.5 Consent Process

The study cardiology fellow or cardiologist will obtain the informed consent from the patient in the Lenox Hill Ambulatory CCTA Clinic. An attempt at outreach will be made for scheduled patients to apprise them of the fact that a study is being conducted. Consent will be obtained on the days of the study. Before consent is obtained, the cardiologist or cardiology fellow will review the major activities of the study with the patient, provide an opportunity for the patient to ask questions, and ask the patient to sign the consent. The patient will receive a copy of the informed consent form (attached), explaining the procedure. Signed informed consent forms will be maintained by the Study Coordinator.

We would like to request a waiver of consent and HIPAA Authorization for the retrospective chart review portion of the study. There will be no intervention, testing, or contact with subjects included in this portion. Only the minimum amount of data required for a robust comparison of event rates will be collected. The retrospective portion of the study meets the criteria for a complete waiver of consent 1) The research involved no more than minimal risk as it simply involves the collection and analysis of previously collected health information of patients who underwent CCTA and invasive cardiac catheterization. 2) The waiver will not adversely affect the rights or welfare of participants because, given that the research would

not impact the participant's current or future care; 3) the study could not be practicably conducted without the waiver given the large sample size and the fact that the participants were never or are no longer patients of the PI. It is also possible that the subjects are now deceased or no longer part of the Northwell system. 4) The outcome of the chart review will not impact the future care of participants so no additional information will be provided to them. The study will protect the identifiers by storing information in REDCap.

PHI (date of procedure and participant name) is required for the conduct of the retrospective portion of the study as the researchers will need to access the charts of individuals who meet study criteria in order to collect the test results of interest.

No study participants under the age of 18 will be recruited.

Cognitively impaired subjects will not be recruited, due to the need for the subjects to be capable of following the technologist's instructions during the CCTA exam.

If the study will enroll non-English speaking subjects:

The study does not target non English speaking populations. However, we will utilize Northwell approved short forms combine with HIPAA authorization forms translated in the appropriate language as necessary to ensure that the subject can provide appropriate consent.

7.6 Early Withdrawal of Subjects

7.6.1 When and How to Withdraw Subjects

Subjects may withdraw from the study for any reason at their request. Subjects who cannot or will not cooperate with the CCTA technologists instructions will be withdrawn from the study, because we will not be able to perform a CCTA. For some subjects, FFR results may not be available due to poor quality of CCTA scan. In this case, the subject will remain in the study, following standard of care, but no FFR reading will be available. If at any time a patient experiences an adverse reaction to medical care, the procedure will be ended and the patient will be withdrawn from the procedural part of the study. Wherever possible, when patients withdraw from the procedure part of the study (the CCTA) we will make every effort to conduct study follow-up.

7.6.2 Data Collection and Follow-up for Withdrawn Subjects

We will make every effort to conduct study follow up for all subjects, regardless of their ability to receive CCTA and CT-FFR. The study coordinator will make a minimum of 5 attempts to follow up with the subjects by telephone. If this does not work, he will try to contact the patients 3 times by email, if patient contact information is available, and once by U.S. postal service certified mail. The team will also check records for follow up at Lenox Hill Hospital and will review death registries to ascertain whether the patient is still alive.

8 Study Drug/Device

8.1 Description

The agent in this study is the computer program that provides the CT-FFR interpretation of flow. This is not an investigational agent, having been approved by the IRB in November 2014. The results will allow the physician to visualize flow through the coronary arteries and measure the level of obstructive disease. The physician will dictate a report based on his/her interpretation of the images. The report and a portable document format (pdf) file of a major view of the coronaries will be maintained as part of the patient's medical record.

8.2 Treatment Regimen

The CCTA data will be collected as part of the standard of care delivered for patients undergoing CCTA with contrast.

8.3 Method for Assigning Subjects to Treatment Groups

This is not a randomized study. Treatment assignments will follow the clinical protocol.

Once the CCTA results are interpreted by the physician, the physician will order CT-FFR exams for patients whose level of stenosis by CCTA standards is 30% to 100%.

If CT-FFR is positive patients will be referred for Cardiac Catheterization and invasive FFR.

If CT-FFR is negative, and level of obstruction is 30 to 49% by CCTA standards, patients will be referred to optimal medical care.

If CT-FFR is negative and level of obstruction is 50% to 70% by CCTA standards, patient will be referred for stress MPI. If stress MPI is positive patients will be referred for Cardiac Cath and invasive FFR. If stress MPI is negative, patients will be referred to optimal medical care.

If the patient has had a stress MPI within one year of the CCTA exam and the CCTA exam result is 50% to 70% obstructive, the physician will rely on the prior stress testing result, rather than repeating the stress test. If the stress testing results was negative, the patient will be referred to optimal medical care. If, in the investigator's opinion, the results indicate that the patient is at increased risk of obstructive disease, when considered with the CCTA findings, the patient will be referred to Cardiac Cath and Invasive FFR.

If CT-FFR is negative and level of obstruction is 70% to 100% by CCTA standard, patient will be referred to Cardiac Cath and Invasive FFR.

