Methodology	Prospective clinical trial
Study Duration	15 months
Study Center(s)	Single center
Objectives	The purpose of this study is to evaluate the incremental benefit of Fractional Flow Reserve (FFR) derived from Coronary Computed Tomographic Angiography (CCTA) (CT-FFR) compared to CCTA with or without stress testing, using invasive FFR as the gold standard for patients with obstructive disease (> 30% stenosis). This study will also assess the capability of CT-FFR to enhance performance on both negative and positive predictive value for less experienced readers by providing feedback based on CT-FFR evaluation
Number of Subjects	Number of subjects projected for the entire study 572
Diagnosis and Main Inclusion Criteria	Chest Pain and stable angina patients with suspicion of coronary artery disease
Study Product, Dose, Route, Regimen	n/a. The study will assess the capability of measuring fractional flow reserve noninvasively utilizing computers and information provided by routine CCTA studies.
Duration of administration	n/a
Reference therapy	The standard reference will be invasive FFR.
Statistical Methodology	Defining an event as performance of ICA when no intervention is necessary, we expect to compare event rates for patients treated with CCTA and FFR-CT, using t-tests and a multivariate, risk adjusted 90 day hazard model with 95% confidence interval. Our null hypothesis is that outcomes will not vary regardless of which testing is used to assess obstructive disease. Our alternative hypothesis is that evaluation with FFR-CT as oppose to CCTA alone will reduce the event rate. We will assess the comparability of the CCTA readers' readings and compare them to the CT-FFR results and the noninvasive FFR results.

1 Previous Study History

Has this study ever been reviewed and rejected/disapproved by another IRB prior to submission to this IRB?

No Yes – if yes, please explain:

2 Brief Summary of Research

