6.1 General Design

This will be a prospective clinical trial designed to evaluate the incremental benefit of virtual FFR measured from CCTA, compared to invasive FFR and CCTA for the detection of flow-limiting coronary stenosis, as defined by invasive FFR ≤ 0.8 and vessel diameter of $\geq 2\text{mm}$.

572 consecutive patients who present to Lenox Hill Hospital Outpatient Clinics for CCTA due to chest pain or stable angina over a ten month period and meeting the study inclusion criteria are eligible for the study (Figure 1). Our team will employ CCTA-appropriateness criteria to ensure proper selection of patients, derived from the Appropriate Use Criteria for Cardiac Computed Tomography published in 2010 and jointly authored by multiple societies including ACCF, SCCT, and ACR [10]. FFR-CT measurements will be performed by a core laboratory in a blinded fashion. All eligible patients will undergo 64-slice or greater multi detector CCTA and CT-FFR measurements. The severity of the stenosis will be determined on site by level III CCTA readers. Patients with obstructive lesions of (30% to 100% stenosis) will receive Stress-MPI, per SOC protocol, and CT-FFR. Patients with positive Stress-MPI and CCTA (50% - 70%) or positive CCTA (71% to 100%) will undergo ICA with invasive FFR measurement in accordance to accepted guidelines and established practice standard. Those patients with invasively measured FFR ≤ 0.8 and with vessel diameter of $\geq 2\text{mm}$, or those who require revascularizations based on invasively estimated stenosis severity will be considered to have flow-limiting obstructive CAD, while the rest will be considered to have non-flow limiting obstructive CAD (if also $>50\%$ stenosis on ICA). If stenosis severity turns out to be $< 50\%$ after ICA (the gold standard), we will conclude that these patients have non-obstructive CAD. (Figure 1). Patients with 30% to 49% obstructive disease, according to CCTA, will be referred to optimal follow up care only. Any in this group who have positive CT-FFR will return for

ICA with invasive FFR measurement, and follow the protocol for those with 50% to 100% obstruction.

Figure 1:

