6.2 Primary Study Endpoints

Defining an event as performance of ICA when no intervention is necessary, we expect to compare event rates for patients treated with CCTA and FFR-CT, using t-tests and a multivariate, risk adjusted 90 day hazard model with 95% confidence interval. Our null hypothesis is that outcomes will not vary regardless of which testing is used to assess

obstructive disease. Our alternative hypothesis is that evaluation with FFR-CT as oppose to CCTA will change the event rate. We will also correlate noninvasive and invasive FFR studies.

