*Patients who have borderline obstructive disease (50% to 70% stenosis) who have negative CT-FFR will be referred for Stress MPI to confirm, unless the patient has had stress testing within a year of the CCTA. This is an accepted practice as part of the standard of care at Lenox Hill Hospital. If the stress test is negative, the patient will be referred to his/her physician for follow-up. If the stress test is positive, the patient will be referred to Invasive Coronary Angiography for Invasive FFR and diagnostic cardiac catheterization. If the patient has had a history of negative stress testing within a year of the CCTA, then the patient will be referred to his/her physician for follow-up. If the patient's prior stress test had findings that, in the investigator's opinion, increase the patient's risk of obstructive disease when viewed with the CCTA findings, the patient will be referred to Invasive Coronary Angiography for diagnostic cardiac catheterization and Invasive FFR. This is an accepted practice as part of the standard of care at Lenox Hill Hospital.**

Patients who have borderline obstructive disease (50% to 70% stenosis) who have positive FFR will be referred for Invasive Coronary Angiography for Invasive FFR and diagnostic

*cardiac catheterization. This is an accepted practice as part of the standard of care at Lenox Hill Hospital. **

Patients with 71% or greater stenosis will be referred for Invasive Coronary Angiography for Invasive FFR and diagnostic cardiac catheterization. This is an accepted practice as part of the standard of care at Lenox Hill Hospital.

**In current standard of care practice at Lenox Hill Hospital, for borderline obstructive coronary disease, the decisions as to whether to proceed with stress testing or refer to invasive coronary angiography is left to the medical discretion of the attending cardiologist.*

Invasive Coronary Angiography and Invasive FFR are considered to be the gold standard procedures for evaluation of obstructive coronary artery disease. Patients deemed to be at high risk for obstructive disease based on CCTA or Stress testing are referred for invasive testing to determine whether cardiac intervention consisting of Percutaneous Coronary Intervention or Coronary Artery Bypass Graft is necessary.

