If patient receives a stress MPI, and it is negative, visit 3 will be referral to optimal follow-up care.

If patient receives a stress MPI, and it is positive, visit 3 will be to cardiac cath and invasive FFR.

If patient undergoes a cardiac cath and invasive FFR at visit 2, visit 3 will be a referral to optimal follow-up care.

Visit 4: If patient receives a cardiac cath with invasive FFR at visit 3, visit 4 will be to optimal follow-up care.

10 Risks to Subjects

The risks to subjects in this study are minimal, compared to the risks faced by the population of patients receiving standard of care for potential coronary artery disease and stable chest pain or angina at Lenox Hill Hospital. Most patients will receive the standard of care currently in place, but will have an additional test run (CT-FFR). This test does not require any additional activity of the patient beyond completion of the CCTA with contrast (Standard of Care). This test will be used to assess whether improvements in the standard of care can be made for future patients.

A small percentage of patients, those who have positive CT-FFR, but 30 to 49% obstructive disease by CCTA standard will undergo an additional invasive exam. This exam may identify obstructive disease. If so, the patient will benefit. If not, the patient will undergo an invasive procedure unnecessarily. We believe that very few patients, if any, will fall into this category.

Patients who undergo Invasive FFR and Diagnostic Cardiac Catheterization will face increased risk, as compared to standard of care. According to the NIH National Heart Lung and Blood Institute, this procedure is very common, and rarely causes serious problems. [22] However, complications can include bleeding, infection and pain at the catheter insertion site. On rare occasions the catheter can scrape or poke a hole in a blood vessel during insertion

causing damage to the blood vessel. Patients may also experience an allergic reaction to the dye that is used during the procedure. Less common reactions include arrhythmias, or irregular heart beats; kidney damage caused by the dye that is used during the procedure; blood clots that can trigger stroke or heart attack or other serious problems; low blood pressure; or a buildup of fluid in the sac that surrounds the heart. This may cause the heart not to beat properly. [22]

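### Against the Section 6.1 referral rule CT-FFR adds angiographies and averts none, so a lower negative-ICA share than in historical controls would not show that CT-FFR averted procedures

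*Combined protocol and SAP*

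**What the plan says.** **Endpoint and hypothesis.** Section 6.2 sets the primary event: "Defining an event as performance of ICA when no intervention is necessary". The Study Summary states a directional alternative, that "evaluation with FFR-CT as oppose to CCTA alone will reduce the event rate". Section 6.2 states a non-directional one, that "evaluation with FFR-CT as oppose to CCTA will change the event rate". Sections 10 and 11 expect CT-FFR to bring substantial reductions in catheterisation without intervention.

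**Referral by CCTA and MPI.** Section 6.1: "Patients with positive Stress-MPI and CCTA (50% - 70%) or positive CCTA (71% to 100%) will undergo ICA with invasive FFR measurement". Patients at 30–49% get follow-up care only, unless CT-FFR is positive.

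**Study pathway.** Section 8.3 refers all CT-FFR-positive patients to ICA. With a negative CT-FFR there is no ICA at 30–49%, and stress MPI (or a stress MPI from the past year) decides at 50–70%. At the top, "If CT-FFR is negative and level of obstruction is 70% to 100% by CCTA standard, patient will be referred to Cardiac Cath and Invasive FFR". Visit 2 in Section 9.2 follows the same scheme.

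**Current practice.** A footnote in Section 9 leaves the choice at borderline stenosis to the treating physician: "decisions as to whether to proceed with stress testing or refer to invasive coronary angiography is left to the medical discretion".

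**Comparator and powered rate.** Controls are ICAs from 2014 to 2018 performed for a positive stress test and/or a positive CCTA (6.1, 7.4, 9). Section 14.1 powers the share of negative results among ICA patients, 14% against 6%, with 121 ICAs.

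**Added procedures.** Of CT-FFR-positive patients at 30–49%, Sections 10 and 11 say: "We believe that very few patients, if any, will fall into this category".

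**The concern.** The stated benefit is fewer angiographies that lead to no intervention. For CT-FFR to deliver it, a negative CT-FFR must keep some patients out of the catheterisation laboratory who would otherwise have gone. As written, a positive CT-FFR opens a new route to ICA, while a negative one leaves the decision where CCTA and stress MPI had already put it.

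The comparison cannot make up for this. The control series has no denominator of tested patients, so procedures that did not take place cannot be seen in it. The powered quantity is a proportion among people who had ICA. It can fall because more positive ICAs were added, or because the historical patients differ. Controls may, for example, have been catheterised on a stress test with no CCTA at all. A reader of the final report could take such a fall as evidence that CT-FFR spared patients an invasive procedure.

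**Working it through.** **1. The plan's own figure.** Inputs from 14.1: p0 = 0.14, p1 = 0.06, two-sided 0.05, power 80%, one-sample test.

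n = [1.96·√(0.14·0.86) + 0.8416·√(0.06·0.94)]² / (0.14 − 0.06)² = 120.99, so 121. Then 121 / (0.60·0.35) = 576.2, so 576, and 576 + 18 = 594. The figures in 14.1 reproduce.

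**2. Who is sent to ICA.** Three stenosis bands × CT-FFR × MPI give 12 cells. The 6.1 column is the CCTA/MPI rule with CT-FFR left out. The last column is direct referral at 50–70%, which the Section 9 footnote permits.

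| CCTA band | CT-FFR | MPI | Cells | 6.1 rule | 8.3 pathway | Direct ICA at 50–70% |
|---|---|---|---|---|---|---|
| 30–49% | − | either | 2 | no | no | no |
| 30–49% | + | either | 2 | no | ICA | no |
| 50–70% | − | − | 1 | no | no | ICA |
| 50–70% | − | + | 1 | ICA | ICA | ICA |
| 50–70% | + | − | 1 | no | ICA | ICA |
| 50–70% | + | + | 1 | ICA | ICA | ICA |
| 71–100% | either | either | 4 | ICA | ICA | ICA |

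- Against the 6.1 rule, 8.3 averts ICA in 0 cells and adds it in 3.
- Against direct ICA at 50–70%, it averts ICA in 1 cell (CT-FFR negative, MPI negative) and adds it in 2.

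**3. The averting cell.** Number averted = (CT-FFR-negative patients at 50–70%) × (share who would have gone straight to ICA) × (share of those who are MPI-negative). The documents give none of the three. The result runs from 0, if nobody is referred directly, to every MPI-negative patient in the cell. The negative stress test is what closes the route: under the 6.1 rule every MPI-negative patient at 50–70% avoids ICA, whereas under 8.3 only the CT-FFR-negative ones do. A reduction here could not be credited to CT-FFR alone.

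**4. How the powered share could fall with nothing averted (illustration).** Assume no averted ICA, the same case mix, and 14% as the rate without CT-FFR. Let X be the base ICAs and Y the added ICAs, all positive.

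0.14X / (X + Y) = 0.06, so Y = (0.14/0.06 − 1)X = 1.33X. With X + Y = 121, X = 51.9 and Y = 69.1, so 57% of ICAs would have to be added true positives.

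Smaller additions, all positive, with 121 ICAs in total and the normal approximation:

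| Added / base | Negative share | Power |
|---|---|---|
| 5% | 0.14/1.05 = 13.3% | about 4% |
| 10% | 0.14/1.10 = 12.7% | about 5% |
| 25% | 0.14/1.25 = 11.2% | about 12% |

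The largest count significantly below 14% is 9/121 = 7.4% (z = −2.08); 10/121 gives z = −1.82.

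**5. Does Aim 1 fill the gap?** Section 14.2 counts the combined test as positive whenever ICA is required. Every patient whom the protocol sends to ICA is then test-positive, including CT-FFR-negative patients above 70%. The CT-FFR result itself is never classified against ICA. Section 6.2 promises only a correlation of noninvasive and invasive FFR.

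**The case against.** A reader might infer that CT-FFR can never avert an ICA and that the primary hypothesis cannot be demonstrated. The documents do not support either statement.

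- The 6.1 sentence describes what study patients undergo. The planned comparator is historical practice, in which the Section 9 footnote allows direct referral of borderline patients, and a positive CCTA alone is a qualifying indication for controls. Against that practice one cell is averted.
- The powered quantity is a proportion of ICAs, and it can fall. Section 6.2 also states a non-directional alternative. The difficulty is what a fall would mean, not whether one can occur.
- The 12 cells omit the branch for a stress MPI within the past year, where referral rests on the investigator's opinion, and Section 8.9.1 lets cardiologists base final recommendations on the CT-FFR images. Strict containment of the 6.1 set within the 8.3 set is therefore not proved for every patient. Figure 1 is not available to settle it.
- Section 14.1 labels the 14% as the rate for CCTA plus CT-FFR, so it is not a documented rate without CT-FFR. The remark about very few patients covers only 30–49%; the number added at 50–70% with positive CT-FFR and negative MPI is not given. The 69-of-121 figure is therefore an illustration and not an estimate.

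All four points stand, and they limit the claim to one of attribution. They do not rescue the reduction claim, because the one averting route also needs a negative stress test and the control series cannot show averted procedures.

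**Conclusion.** The point holds as one about interpretation of the primary comparison. Against the 6.1 rule, 8.3 averts no ICA and adds ICAs in CT-FFR-positive patients at 30–49%, and at 50–70% with negative MPI. Averting is possible only at 50–70%, against discretionary direct referral and with a negative stress test, at an unknown frequency. A lower negative share than in catheterised controls would thus not show that CT-FFR averted procedures, which is the claim in the Study Summary and Sections 10 and 11.

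The size of the gap depends on assumptions. If nothing is averted, case mix is equal and 14% is the base rate, the planned 6% needs 1.33 added, all-positive ICAs for each base ICA. With additions of 25% or less, power is about 12% or lower. The cell count rests on the text of 6.1 and 8.3 and leaves out the prior-stress-test branch.

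**What to change.** Care stays as it is.

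1. State in 6.2 and 14.2 that the comparison with historical ICAs does not estimate ICAs averted by CT-FFR. Limit the conclusion, and the wording in the Study Summary and Sections 10 and 11, accordingly.
2. Pre-specify an analysis of the CT-FFR result itself, not of whether ICA was required, against the ICA/invasive FFR reference in patients above 70% stenosis, who are referred whatever CT-FFR shows. Report the negative ICAs that a negative CT-FFR would have averted and the positive ICAs it would have missed, with exact 95% confidence intervals. Also report how many patients in the band lack a CT-FFR or an ICA result.
3. Report CT-FFR-negative, MPI-positive patients at 50–70% separately and descriptively, as the share with a negative ICA. They are all CT-FFR-negative, so pooling them into sensitivity or specificity would select on the test result.
4. Reconcile Sections 6.1, 8.3, 9 and 9.2, which differ on 50–70% with positive CT-FFR and negative MPI, and on exactly 70% stenosis.

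The cost is protocol and SAP wording plus a small set of tables from data already collected. Section 14.1 refers to screen failures in the past tense, so enrolment may have begun; the addition should be dated before CT-FFR is tabulated against ICA. The headline claim becomes more modest. Precision will be limited, since the plan does not say how many of the 121 ICAs fall above 70%, and the result applies to that band only. Replacing the primary comparison outright would need a new sample size and is not asked for here.
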